# **Dermatological (Skin) Examination**

Dermatological (skin) evaluations will be performed as part of the physical exam at screening, and then every 6 months in Part A and yearly in Part B, as scheduled in Table 1 and Table 2 (Part A), and Table 3 and Table 4 (Part B). Dermatological (skin) evaluations will be performed by the treating investigator or medically qualified designee. Patients with any suspicious finding noted during the examination will be referred to an appropriately qualified dermatologist for evaluation and treatment, if warranted.

#### **Suicidality Assessment**

Suicidality will be assessed using the C-SSRS (Posner, 2011) at all study visits during Part A and Part B. It will be self-administered through a validated IVRS.

#### **Monitoring of AEs and SAEs**

Throughout the course of the study, Part A (both periods) and Part B, every effort must be made to remain alert to possible AEs or SAEs. Refer to Section 12 for definitions of AEs/SAEs, monitoring and reporting. Refer to Section 12.4 for AEs of special interest.

#### **Monitoring of Concomitant Therapy**

The use of concomitant medication and procedures will be monitored throughout the study in Part A (both periods) and Part B. Refer to Sections 9.5.7 and 9.5.8 for prohibited concomitant therapies.

#### 11.2.2. Laboratory Safety Assessments

will analyze the samples. Further details of the procedures to be followed for sample collection, storage, and shipment will be documented in a laboratory manual.

Additional and repeat laboratory safety testing may be performed at the discretion of the Investigator.

The following laboratory tests will be performed to assess the safety profile of RPC1063:

#### • Routine safety laboratory tests:

- Hematology RBC count, total and differential WBC count (basophils, eosinophils, lymphocytes, monocytes, and neutrophils), platelet count, hemoglobin, hematocrit, MCV, MCH, and MCHC. Total WBC and all differential WBC counts will be blinded information for the treating investigator after the onset of study treatment.
- Chemistry sodium, potassium, chloride, calcium, magnesium, phosphate, blood urea nitrogen, random glucose, hemoglobin A1c, albumin, alkaline phosphatase, creatinine, SGPT/ALT, SGOT/AST, GGT, amylase, total bilirubin, conjugated bilirubin as scheduled in Table 1 and Table 2 (Part A), and Table 3 and Table 4 (Part B). In addition, the following parameters will be assessed at baseline and every 6 months of Part B: total cholesterol, triglycerides, HDL and LDL. Abnormal laboratory parameters inconsistent with clinical presentation of MS or suspicious of underlying medical condition should be repeated for accuracy. If an increase of amylase above the clinically notable value (≥ 300 U/L) is observed at any post randomization visit, lipase should be tested to determine the origin of elevated amylase (pancreatic versus extra pancreatic)
- Urinalysis leukocytes, specific gravity, bilirubin, blood, glucose, ketones, pH, protein, and urobilinogen
- The central laboratory will analyze routine blood samples. Blood samples taken at the screening visit are to be in the fasting state. Blood samples taken at subsequent visits are recommended to be in the fasting state. Details regarding collection of samples, shipment of samples, reporting of results, laboratory reference ranges, and alerting abnormal values will be supplied to the site before site initiation in a study laboratory manual. The results of the analysis will be made available to each site by the central laboratory, at the earliest, 48 hours after receipt of the samples by the central laboratory.
- Investigators will be asked to comment on those abnormalities on the respective laboratory result page, including a notation of the clinical significance of each abnormal finding in the patient's source documents. The laboratory sheets will be filed with the patient's source documents. Abnormal laboratory values should not be recorded on the AE eCRF; however, any diagnoses (or signs or symptoms if a diagnosis is not possible) associated with the abnormal findings should be recorded on the AE eCRF.
- Pregnancy test: serum beta-hCG must be performed at screening (Part A and Part B) in women of childbearing potential; urine beta-hCG will be performed in women of childbearing potential at each visit (Part A and Part B), and if positive, do not dose, and confirm with a serum pregnancy test.
- Coagulation panel: PT and PTT. To be performed at screening, at Week 24/end of study of Part A and Month 24/end of study of Part B, and at follow-up visits.
- sTSH: To be performed at screening, at Week 24/end of study of Part A, and yearly during Part B.

- Serology testing will be performed at screening of Part A and Part B to determine the patient's immune status with respect to the following viruses:
  - VZV
  - HIV antibodies
  - anti-hepatitis A virus IgM
  - HBsAg and HBcAg IgM
  - anti-HCV IgG or IgM.

Patients who are negative for VZV IgG antibodies at screening can undergo appropriate varicella zoster vaccination and be enrolled 30 days after vaccination has been completed. Patients testing positive for HIV or for serological markers of acute or chronic hepatitis A, B, or C will be excluded from the study unless they are indicative of prior hepatitis B vaccination or cured hepatitis A or B and accompanied by normal liver transaminase values.

- Syphilis RPR: Patients must have a negative RPR result to be enrolled or, in the event of a false positive result on RPR, a negative treponeme-specific test performed at the central laboratory.
- TB test: to be assessed using the purified protein derivative test, QuantiFERON Gold, or other interferon gamma release assay (as locally available), and CXR at screening of Part A and Part B. All testing must be completed prior to administration of study drug on Day 1.

#### 11.2.3. PK and PD Assessments

PK samples will be shipped to . Details of the procedures to be followed for sample collection, storage, and shipment will be documented in a separate PK Laboratory Manual.

The following PK and PD assessments will be performed:

- Standard PK sampling: PK samples are to be taken predose or at 2 to 6 hours postdose following administration, as indicated in the Schedule of Events
- Plasma protein biomarker analysis (cytokines, chemokines, other inflammatory proteins)
- Total Igs: IgA, IgG, IgM

The bioanalytical assay for the determination of RPC1063 and its metabolites RP101075, RP101442, and RP101988 in  $K_2$  EDTA human plasma utilizes a liquid/liquid extraction with ultra performance liquid chromatography (UPLC) separation and Tandem Mass Spectrometry (MS/MS) detection. Quantification is achieved using analyte peak area to internal standard peak area. For each analyte, a stable labeled version (tri-deuterium) was used as the internal standard. The method was validated for the concentration range of (RPC1063 and RP101075), (RP101442), and (RP101988). The method was demonstrated to be selective, precise and accurate for analysis of RPC1063 and its metabolites in human plasma. The assay performance is not affected by hemolysis or lipemia.

RPC1063 and its metabolites were shown to be stable for at least 31 days at -70°C in human plasma and a long term stability program (-20°C and -70°C) is in progress.

## 12. SAFETY DEFINITIONS, MONITORING, AND REPORTING

Throughout the study, the Investigator will remain alert to possible AEs. If an AE occurs, the first concern should be for the safety of the patient and appropriate medical intervention should be provided if necessary.

At the signing for the informed consent form, patients should be given names and telephone numbers of site staff for reporting AEs and medical emergencies.

## 12.1. Adverse Events (AEs)

The AE definitions and reporting procedures provided in this protocol comply with current CFR 21 Part 312. An AE is any untoward medical occurrence that does not necessarily have a causal relationship with the investigational medicinal product. An AE can therefore be any unfavorable or unintended sign, including an abnormal laboratory finding, symptom or disease temporally associated with the use of an investigational medicinal product whether or not considered related to the investigational medicinal product.

Relapses and MS disease progression will be monitored as study endpoints, but will not be recorded as AEs.

AEs will be monitored throughout the entire study. Investigators will ask the patient at each visit if they have experienced any untoward occurrence since the last study visit. All AEs will be recorded on the eCRFs provided: a description of the event, severity, time of occurrence, duration, any action (e.g. treatment and follow up tests) and the outcome should be provided along with the Investigator's assessment of the relationship to the study treatment.

AEs will be recorded from the start of study drug treatment until 28 days following the last dose of treatment with the study drug.

If known, the event diagnosis should be recorded rather than listing individual signs or symptoms. AEs must be graded as being mild, moderate or severe and their approximate duration given. Definitions of severity are as follows:

Mild: an AE usually transient in nature and generally not interfering with normal activities;

Moderate: an AE that is sufficiently discomforting to interfere with normal activities;

Severe: an AE that is incapacitating and prevents normal activities.

Even if the Investigator feels there is no relationship to the study drug, all AEs MUST be recorded in the eCRF. The Investigator is requested to assess the relationship of any AEs to treatment using the following definitions:

Unrelated: those AEs which are clearly and incontrovertibly due to extraneous causes (concurrent drugs, environment etc.) and do not meet the criteria for drug relationship listed under Unlikely, Possible, Probable or Related.

Unlikely: an AE may be considered unlikely if it includes at least the first two features:

• It does not follow a reasonable temporal sequence from administration of the drug.

- It could readily have been produced by the patient's clinical state, environmental or toxic factors, or other modes of therapy administered to the patient.
- It does not follow a known pattern to the suspected drug.
- It does not reappear or worsen when the drug is re-administered.

Possible: an AE may be considered possible if it includes at least the first two features:

- It follows a reasonable temporal sequence from administration of the drug.
- It could readily have been produced by the patient's clinical state, environment or toxic factors, or other modes of therapy administered to the patient.
- It follows a known response pattern to the suspected drug.

Probable: an AE may be considered probable if it includes at least the first three features:

- It follows a reasonable temporal sequence from administration of the drug.
- It could not be reasonably explained by the known characteristics of the patient's clinical state, environmental or toxic factors or other modes of therapy administered to the patient.
- It disappears or decreased on cessation or reduction in dose. There are exceptions when an AE does not disappear upon discontinuation of the drug (e.g. bone marrow depression, fixed drug eruptions, tardive dyskinesia, etc).
- It follows a known pattern of response to the suspected drug.

Related: an AE may be considered related if it includes all of the following features:

- It follows a reasonable temporal sequence from administration of the drug.
- It could not be reasonably explained by the known characteristics of the patient's clinical state, environmental or toxic factors or other modes of therapy administered to the patient.
- It disappears or decreased on cessation or reduction in dose. There are exceptions when an AE does not disappear upon discontinuation of the drug. For example: bone marrow depression, fixed drug eruptions, tardive dyskinesia, etc.
- It follows a known pattern of response to the suspected drug.
- It reappears or worsens if the drug is re-administered.

# **12.2.** Serious Adverse Events (SAEs)

An SAE is any untoward medical occurrence or effect that fulfills the following criteria:

- Results in death
- Is life-threatening (NOTE: the term "life-threatening" refers to an event in which the patient was at risk of death at the time of the event; it does not refer to an event which hypothetically might have caused death if it were more severe)
  - o Requires hospitalization or prolongation of existing inpatient hospitalization

01 October 2014 Version 4.0

- Results in persistent or significant disability or incapacity
- Is a congenital abnormality/birth defect
- Important medical events not captured by the above but which may, for example, require medical intervention to prevent one of the outcomes above.

Medical and scientific judgment should be exercised in deciding whether expedited reporting is appropriate in other situations, such as important medical events that may not be immediately life-threatening or result in death or hospitalization but may jeopardize the patient or may require intervention to prevent one of the other outcomes listed in the definition above. These should also usually be considered serious. Examples of such events are intensive treatment in an emergency room or at home for allergic bronchospasm; blood dyscrasias or convulsions that do not result in hospitalization; or development of drug dependency or drug abuse.

Uncomplicated cases of relapse and MS disease progression requiring hospitalization or otherwise meeting the above serious criteria do not need to be reported as SAEs, unless there are other diagnoses or complications which meet serious criteria.

# 12.3. Reporting of Serious Adverse Events

Full

details of the procedures to be adopted will be documented in a safety management plan approved by responsible parties, in brief:

The Investigator will report any SAE that occurs to any patient from the time written informed consent is signed through the last visit. All SAEs that occur within 28 days of the last dose of treatment with the study drug, whether or not considered related to the investigational product, must also be reported. Any SAE that is ongoing when the patient completes the study or discontinues from the study will be followed by the Investigator until the event has resolved, stabilized, or returned to baseline status.

Any AE considered serious by the Investigator or Sub-investigator or that meets serious criteria should be reported to using the remote data capture (RDC) system. Data entry must be completed within 24 hours from the time the study site personnel first learned of the event.

In the event that RDC entry is not possible (e.g. system failure or access problems), the study site should complete the paper SAE report form and fax the form to within 24 hours of awareness of the event. The RDC system should be updated as soon as it is available.

Contact information for the	
CX	

Refer to Study Operations Manual for local phone numbers.

The initial report should be promptly followed by detailed, written reports, which will include copies of hospital case records, discharge summaries, autopsy reports and other documents when

requested and applicable. For unrelated cases, a full detailed case description may negate the need for additional hospital case records, discharge summaries etc.

## **12.4.** Monitoring of Patients with Adverse Events

Investigators must carefully monitor each patient for AEs. This includes clinical laboratory variables. Assessments must be made of the seriousness, severity and relationship to the administration of the study treatment. After the initial AE/SAE report the Investigator is required to follow up proactively each patient and provide further information to on the patient's condition. During the study all AE/SAEs should be followed up to resolution unless the event is considered by the Investigator to be unlikely to resolve due to the patient's underlying disease, or the patient is lost to follow up.

## Monitoring of Patients with Adverse Events of Special Interest

Several of the AEs noted in fingolimod clinical studies may be a consequence of S1P1R stimulation and will therefore be closely monitored in the RPC01-201 study. These AEs include:

- a. Bradycardia and heart conduction abnormalities. Dose-related transient, reversible bradycardia, symptomatic bradycardia, and first, second, or higher degree atrioventricular block were reported primarily as first dose effects in fingolimod studies. The heart rate reduction observed with sphingosine-1-receptor agonists is an expected effect of S1PR modulation and appears to be conducted through the same pathway as vagus nerve stimulation. In addition, these negative chronotropic effects of S1P1R agonists appear to attenuate over time secondary to S1PR desensitization and internalization on cardiac myocytes (Kovarik 2008). This effect appears to occur with increasing exposures of study drug, thus gradual titration of the dose of RPC1063 over several days may mitigate against larger reductions in HR.
- b. Pulmonary toxicity. An initial sharp decrease followed by a slow progressive decline over time in FEV1 was observed in fingolimod clinical studies. Nonclinical toxicity studies with RPC1063 have revealed the potential for pulmonary toxicity at doses considerably higher than the pharmacologically active dose. FEV1, FVC, and DLCO will be measured in all patients. Every patient whose PFTs are abnormal will be followed until such time as resolution is confirmed or no further improvement is expected by the investigator (based on a follow-up period of not less than 3 months).
- c. Hepatotoxicity. Fingolimod caused frequent, reversible liver enzyme elevations greater than 3-fold above the upper limit of normal in up to 12% of patients; this was a significant cause of cessation of therapy. In this study, clinical chemistry analyses to assess LFTs will be performed. Every patient whose LFTs are abnormal will be followed until values return to baseline.
- d. Macular edema. Instances of serious macular edema were reported in fingolimod renal transplant studies, and a 0.8% incidence was reported as an SAE in fingolimod (1.25 mg dose) MS clinical studies. Nonclinical studies with RPC1063 have not revealed eye-related toxicities. In this study, measurement of central foveal thickness by OCT will be performed in all patients. For patients

with abnormal OCT findings or with visual signs or symptoms of macular edema, a general ophthalmologic examination including eye history, visual acuity, and dilated ophthalmoscopy will also be performed. Every patient whose ophthalmic evaluations reveal abnormalities will be followed until values return to baseline or no further improvement is expected by the investigator (based on a follow-up period of not less than 3 months).

### Overall, the following procedures should be followed:

- Vital signs will be assessed in supine and standing position at every visit. A sudden, significant fall in blood pressure (> 20 mmHg) between 2 and 5 minutes after standing from the supine position will be interpreted as an orthostatic hypotension and will be documented in the patient chart and eCRF.
- Patients will be closely monitored in the clinic after their first dose of the initial dose titration regimen for a period of 6 hours after treatment. ECGs will occur predose and at Hour 6 following dosing, with more frequent assessments as clinically indicated; vital signs, including orthostatic blood pressure assessment, will be assessed predose and then hourly for 6 hours following dosing. See the monitoring guidelines in Section 10.2.1.1 for further details.
- Clinicians should be particularly mindful of patients who have a low pulse at baseline (spontaneously or through drug induced β-receptor blockade), prior to administration of the study drug. Atropine IV is recommended as the first line treatment of bradycardia, up to a maximum daily dose of 3 mg. Furthermore, the common guidelines for treatment of bradycardia (e.g. Advanced Cardiac Life Support-ACLS guidelines) should be followed as appropriate:
  - In case of clinical symptoms or hypotension, administration of atropine 1 mg, repeated administration in 3-5 minutes.
  - If heart rate and/or blood pressure remains unresponsive, consider administration of dopamine drip 5-20 μg/kg/min or epinephrine drip 2-10 μg/min.
  - Performance of transcutaneous pacing may also be considered
  - In the setting of decreased blood pressure, isoproterenol should be avoided or used with caution.
- Any condition that might affect the outcome of pulmonary function testing (FEV1 and FVC) including infection, respiratory symptoms, occupational exposures (including asbestos) and cigarette smoking, needs to be collected before every PFT testing and transcribed to the pulmonary function tests eCRF page. If patients have decline in PFT values (FEV1 and/or FVC) below 50% of the predicted values, treatment should be discontinued. If a patient discontinues due to respiratory AE, the Investigator should ensure that the patient has adequate evaluations as clinically indicated by a pulmonologist (consider pulmonary function tests, chest X-ray or high resolution computed tomography, based on findings of the other exams) at the time of the AE. For patients with pulmonary nodules, lung biopsy should be considered (Cryptococcus pneumonia and pulmonary TB have been reported with fingolimod). Further evaluations will be conducted until such time as resolution is confirmed or no

further improvement is expected by the investigator (based on a follow-up period of not less than 3 months).

- If patients have elevations in the LFTs (SGPT/ALT or/and SGOT/AST) greater than 3 times the ULN, a retest must be performed within 14 days. Upon confirmation of the abnormality, retests should be performed weekly until the elevated LFT decreases to below 3 times the ULN. If the LFT increase is confirmed to be above 5 times the ULN the study medication must be permanently discontinued.
- Study drug must be discontinued in any patient who has a diagnosis of macular edema that is of new onset or worsened since baseline. Patients with a diagnosis of macular edema must be followed up monthly and more frequently if needed based on the ophthalmologist's judgment. Further ophthalmological evaluations will be conducted until such time as resolution is confirmed or no further improvement is expected by the ophthalmologist (based on a follow-up period of not less than 3 months). If the patient does not show definite signs of improvement on examination 6 to 8 weeks after discontinuation of study drug, then therapy for macular edema in conjunction with an ophthalmologist experienced in the management of this condition should be initiated.
- The treating investigator will complete a dermatological (skin) examination for monitoring of the potential development of new cutaneous malignancies during the study. Patients with any suspicious finding noted during the examination will be referred to an appropriately qualified dermatologist for evaluation and treatment, if warranted. Dermatology examinations will be performed at screening, at 6 months for Part A, at 12 months and 24 months for Part B. For patients who discontinue treatment early, a dermatological (skin) examination will be performed at end of treatment.

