## 9.4.4. Withdrawal of Patients from Study Medication and/or the Study

## 9.4.4.1. Discontinuation of Study Medication

Reasons for discontinuation include, but are not limited to the following:

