#### Investigator decision

The Treating Investigator may discontinue study medication if it is determined that it is not safe or in the patient's best interest to receive further treatment. The Medical Monitor should be promptly notified of the decision.

- Noncompliance: after consultation between the investigator, the Medical Monitor, or Study Monitor, and the sponsor when appropriate, a patient may be discontinued from study medication for failure to comply with protocol requirements
- Intercurrent illness: A patient may be discontinued from study medication if, in the judgment of the treating investigator, the patient develops an intercurrent illness or complication that is not consistent with the protocol requirements or that, in any way, justifies discontinuation of study medication.
- Protocol-defined adverse events of special interest (see Section 12.4):
  - Confirmed AST or ALT >5 times the upper limit of the normal range, confirmed upon retest within 14 days of the original lab value (unless determined by the investigator to not be of hepatic origin)
  - o A diagnosis of macular edema, which is new or worsening since baseline
  - o FEV1 or FVC <50% of predicted values
- If the patient becomes pregnant
- Sponsor termination or suspension of the study

All patients who discontinue study medication should complete an Early Termination Visit (see Table 2 [Part A] and Table 4 [Part B]). Unless the patient withdraws consent or is lost to follow-up, they will be asked to undergo a follow-up visit 4 weeks after the last dose for the collection of safety data including lymphocyte recovery and to assess their disease status. Alternative treatment for multiple sclerosis (with the exception of medication given in the context of another clinical trial) can be started, if needed, after the early termination visit.

The reason for discontinuation of study medication will be recorded in the clinical records and the patient's eCRF.

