# 12.5. Procedures to be Followed in the Event of Abnormal Laboratory Test Values

In the event of unexplained abnormal laboratory test values, the tests should be repeated immediately and followed up until they have returned to the normal range and/or an adequate explanation of the abnormality is found. Abnormal laboratory values or test results constitute AEs only if they induce clinical signs or symptoms, are considered clinically significant, or require therapy. For abnormal laboratory test values related to AEs of special interest refer to Section 12.4.

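### Protocol 12.4 makes stopping mandatory for any confirmed ALT/AST above 5x ULN, while 9.4.4.1 exempts rises judged non-hepatic; nothing says which governs

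*Protocol*

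**What the plan says.** Two sections of the protocol say when a liver enzyme rise ends study treatment.

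- **Section 9.4.4.1 (Discontinuation of Study Medication)** opens its list with "Reasons for discontinuation include, but are not limited to the following". Under adverse events of special interest it names three criteria and points the reader to Section 12.4. The liver criterion is AST or ALT above 5x ULN, confirmed on a retest within 14 days, with the qualifier "unless determined by the investigator to not be of hepatic origin".
- **Section 12.4 (monitoring of adverse events of special interest)** introduces its bullets with "Overall, the following procedures should be followed". The liver bullet requires a retest within 14 days for ALT and/or AST above 3x ULN, then weekly retests once the rise is confirmed, until the value is below 3x ULN. It ends: "If the LFT increase is confirmed to be above 5 times the ULN the study medication must be permanently discontinued".

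Section 12.5 adds: "For abnormal laboratory test values related to AEs of special interest refer to Section 12.4". The SAP counts patients by LFT category, including 5x ULN and above (10.2.2), and summarises adverse events leading to permanent discontinuation (10.1.5). It sets no stopping rule of its own.

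**The concern.** The enzymes, the threshold and the retest interval are the same in both sections, so they are plainly meant to be one rule. Yet one version lets the investigator's view of origin remove the trigger and the other does not. For a confirmed rise above 5x ULN judged non-hepatic, a site working from 9.4.4.1 could keep the patient on drug, while a site working from 12.4 has to stop permanently.

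What is at stake is uniform patient protection. Hepatotoxicity is named as an adverse event of special interest, and Section 12.4 itself records that fingolimod caused elevations above 3x ULN in up to 12% of patients. The rule applies to every arm of both parts. The exception, as written, asks for neither a recorded cause nor Medical Monitor agreement before dosing continues above 5x ULN. A smaller consequence is that uneven application could slightly alter the summary of adverse events leading to discontinuation.

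**Working it through.** No sample size, power or alpha figure is involved, so the check is a comparison of the two texts.

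**Step 1. Compare the elements of the rule.**

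| Element | 9.4.4.1 | 12.4 |
|---|---|---|
| Enzymes | AST or ALT | ALT and/or AST |
| Threshold | above 5x ULN | above 5x ULN |
| Confirmation | retest within 14 days | retest within 14 days |
| Non-hepatic exception | yes, investigator's judgement | none |
| Consequence | listed reason to discontinue | permanent discontinuation, mandatory |

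**Step 2. Work through the possible cases.**

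| Case | 9.4.4.1 | 12.4 | Result |
|---|---|---|---|
| (a) Confirmed above 5x ULN, origin hepatic or undetermined | stop | stop | consistent |
| (b) Confirmed above 5x ULN, judged non-hepatic | trigger lifted | stop permanently | conflict if dosing continues |
| (c) Above 5x ULN, not confirmed on retest | no trigger | no trigger | consistent |

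The conflict is confined to case (b). Stopping satisfies both sections even there, because the 9.4.4.1 list is not exhaustive.

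**Step 3. Compare the other special-interest criteria in 9.4.4.1 with 12.4.**

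- Macular edema: 9.4.4.1 has "A diagnosis of macular edema, which is new or worsening since baseline"; 12.4 has "Study drug must be discontinued in any patient who has a diagnosis of macular edema that is of new onset or worsened since baseline". Same criterion, no exception in either.
- FEV1 or FVC below 50% of predicted: same threshold, no exception in either. Section 12.4 words the action as should here and as must for the liver rule.
- ALT/AST: differs.

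Two of the three criteria match. Only the liver criterion carries an exception in one section and not in the other.

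**Step 4. Look for reconciling text.** The synopsis, Protocol 12.5 and 12.6, and SAP 10.1.7 and 10.2.2 contain nothing that ranks the two sections or repeats the exception.

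**Step 5. Patients under the rule** (Synopsis, Number of Patients).

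- Part A: 3 x 70 = 210 (140 RPC1063, 70 placebo).
- Part B: 3 x 400 = 1,200 (800 RPC1063, 400 IFN beta-1a).
- Total: 210 + 1,200 = 1,410.

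This is the number the rule covers, not the number in case (b). The documents give neither the share confirmed above 5x ULN nor the share of those judged non-hepatic, so the affected number cannot be computed.

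**The case against.** The best defence is that the sections can be reconciled, in either of two ways.

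1. **12.4 governs.** The heading over the three criteria in 9.4.4.1 points to 12.4, and 12.5 does the same for laboratory values. The 9.4.4.1 parenthesis removes one item from an open list and never says that dosing may continue. A site that follows the pointer finds the mandatory rule. This narrows the ambiguity but does not remove it: a pointer is not a statement of precedence, and if 12.4 governs, the parenthesis has no practical function and should go.
2. **9.4.4.1 clarifies 12.4.** Section 12.4 is concerned with hepatotoxicity, so a non-hepatic rise might be thought outside it. The text does not support this: the 12.4 bullet defines the elevation by enzyme value, with no condition on origin.

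It is also fair to say that other controls exist. Investigators must note the clinical significance of abnormal results in source documents (11.2.2), assess relationship to treatment (12.4), and follow unexplained abnormal values to normal or to an adequate explanation (12.5). None of these permits continued dosing above 5x ULN or makes it conditional on anyone's agreement.

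Finally, the exception may be deliberate, and the strict rule would take study drug from a patient whose rise does not come from the liver. That bears on which fix to choose, not on whether the two sections agree.

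**Conclusion.** The inconsistency is real and should be corrected. For a confirmed ALT/AST above 5x ULN judged non-hepatic, 9.4.4.1 lifts the stopping trigger and 12.4 requires permanent discontinuation, so continuing under the first breaches the second. The conclusion rests on the wording alone and needs no numerical assumption.

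Its reach is limited. Hepatic and undetermined cases stop under both sections. Weekly retesting until below 3x ULN and follow-up to baseline apply whichever section is read. The number affected is unknown and probably small, since it takes both a confirmed value above 5x ULN and a non-hepatic judgement. The primary analysis does not change. What remains is a safety stopping rule that can be applied differently depending on which section a site reads.

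**What to change.** State one identical rule in both sections.

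- **Default:** delete the non-hepatic parenthesis from 9.4.4.1, leaving the threshold and the 14-day confirmation. This keeps the stricter rule that 12.4 already imposes.
- **If the sponsor confirms that the exception is intended:** keep permanent discontinuation for any confirmed rise above 5x ULN in both sections, with a single exemption where the investigator judges the rise non-hepatic, records the non-hepatic cause, and obtains the Medical Monitor's agreement before dosing continues. The last two conditions are additions that neither section now contains; they are recommended because the exemption prolongs exposure at a level that otherwise ends treatment.

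The cost is one parenthesis deleted, or one sentence aligned, in an amendment. Sample size, visits and analyses are unchanged. Under the default, a patient with a truly non-hepatic rise loses study drug, as 12.4 already requires.
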